## K. Risks

Identify possible risks to the participant as a result of the research. Consider possible psychological harm, loss of confidentiality, financial, social, or legal damages as well as physical risks. What is the seriousness of these risks and what is the likelihood that they may occur?

The procedures, techniques, equipment, and measures to be used in the proposed study are commonly used in educational and research settings involving human subjects, and are not new, untested, or of questionable safety. Experimenters are aware of the potential for serious adverse events to occur with any type of moderate intensity exercise, but such risks are considered minimal in this population. In addition, the primary focus of this study is decrease in sedentary behavior and increase in walking rather than moderate to vigorous exercise. There is a risk of physical injury during exercise, particularly if participants have little to no previous experience. Fatigue and muscle soreness may also occur in participants who do not normally engage in physical activity. Exercise is associated with a very small risk of serious medical complications including heart attack and sudden death, although this risk is particularly small in healthy older adults. Lastly, protocols currently exist to respond to any adverse events by contacting emergency response personnel and facilitating their arrival to the correct rooms (if the event occurs at the Center).

## Access to private health information

There is a potential risk of breach of confidentiality that is inherent in all research protocols. There is a possibility that if research data were to become generally known, this knowledge could potentially impact a subject's future insurability, employability, or reproduction plans, or have a negative impact on family relationships, and/or in paternity suits or stigmatization.

### Exercise

There are several common risks associated with exercise participation including injury to muscles or joints, especially when initiating an exercise program after a period of being sedentary. Further, there is a minor risk of dehydration or heat exhaustion. More commonly, there is a risk of falling. Based on our considerable experience in walking and balance-based research assessments and interventions in adults, many of whom are much older than the cohort anticipated for enrollment into this study, we are confident that this risk is rare, meaning that it will occur in less than .001% (less than 1 out of 100000) of people in the otherwise healthy adults targeted for this study. This risk will be minimized as we are focusing on walking and reductions in sedentary behavior rather than exercise training. Adverse or unstable cardiovascular or pulmonary response to exercise, including disorders of heart rhythm, heart attack, stroke, or sudden death will be minimized, because assessment of vital signs and history of heart disease are included in our screening procedures, and only those adults with satisfactory results as detailed in our eligibility criteria will be allowed to participate in experimental procedures for this study. As such, we anticipate that this risk is rare. According to American College of Sports Medicine (ACSM) guidelines published in 2000, the risk of myocardial infarction (MI) in symptomatic (categorized with males and females having ventricular arrhythmias) and asymptomatic (without any signs or symptoms indicative of ischemic heart disease) individuals during exercise is less than 0.04%. The risk of death in the same population is less than or equal to 0.01%, and the risk of needing hospitalization (including acute heart attack and/or serious arrhythmia) is less than or equal to 0.2%. The risk of cardiovascular complications occurring during exercise is rare (occurs in less than 1% of people). A retrospective survey by the YMCA revealed 1 death and 1 cardiac arrest per 2,897,057 and 2,253,267 person-hours. To minimize the risk, we are using a *non-exercise estimation of cardiorespiratory fitness* that requires BMI and heart rate measurement only.

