**H. Recruitment Procedures**

Describe the participants you intend to recruit. Provide all inclusion and exclusion criteria. Include age range, number of subjects, gender, ethnicity/race, socio-economic level, literacy level and health (as applicable) and reasons for exempting any groups. Describe how/when/by whom inclusion/exclusion criteria will be determined.

Participants will not be excluded based on sex, race, or ethnicity. If a participant is excluded for any reason, they will be immediately informed that they have not met all criteria and their participation will be discontinued. All interested participants will be selected to participate until the desired number ( $n = 80$  older adults) is reached. We recognize that women in this age group are over-represented relative to men and are also more likely to volunteer for health-related studies. However, we will do our best to recruit 50% women and 50% men in our sample.

Participants will be randomly assigned to one of the two study conditions. Children will not be included since the study is focused on older adults. Potential participants will be screened over the phone for cognitive function and will be assessed by the Telephone Interview of Cognitive Status (TICS) to ensure normal level of cognitive function. Any participant not passing the TICS as 'normal' will be ineligible for further consideration in the study. Participants with implanted devices that are likely to be adversely influenced by MRI will be marked as "MRI-ineligible" but may be able to participate in the remote/behavioral version of the study.

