#### Exclusion Criteria:

- Current or previous formal diagnosis of a DSM-V Axis I or II disorder including Major Depression (not including post-partum depression or anxiety)
- History of major psychiatric illness including schizophrenia
- Current treatment for cancer – except non-melanoma skin
- Neurological condition (MS, Parkinson's, Dementia, MCI) or brain injury (traumatic or Stroke)
- Type I Diabetes
- Type II Diabetes if unstable or controlled by insulin
- Current alcohol or substance abuse
- Current treatment for congestive heart failure, angina, uncontrolled arrhythmia, DVT or other cardiovascular condition
- A blood clot in the legs in the last 2 years
- Myocardial infarction, coronary artery bypass grafting, angioplasty or other cardiac event in the past year
- 
- Regular use of an assisted walking device or significant increase in pain when walking
- Claustrophobia (if opting into MRI)
- Not passing the Telephone Interview of Cognitive Status (TICS) as normal
- Use of any anti-psychotic, anti-depressant, anti-anxiety, and ADD/ADHD medications.
- Not fluent in English
- Contraindications to MRI (if opting into MRI)
- No regular access to a computer with internet
- Involvement in conflicting research studies currently or recently

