#### Screening Procedures:

Screening procedures will involve verbally screening potential participants over the phone. A staff member doing the screening will begin with an overview of the DASH project. The screener will then obtain verbal consent (see telephone script). The telephone script will ask questions regarding potential participants' demographic information such as age and gender along with medical history questions in relation to inclusion and exclusion criteria. The total

time to administer all screening questions is approximately 30 minutes. The telephone screen will also assess level of physical activity via self-reported physical activity. If eligibility is verified, a date and time will be scheduled for a virtual meeting between the participant and a researcher where the formal study consent will be signed. Those individuals that are deemed ineligible from the screening call will have their forms kept in a separate file on REDCap. This information will be used to quantify how many were ineligible from the screening call and reasons for ineligibility.

The criteria will be assessed by one of the listed study personnel. No special expertise is required to evaluate screening responses. If a participant requires exclusion due to information received during a visit, they will be contacted via telephone or email and informed that they have been excluded from further study. The reason provided for their exclusion will be brief, and will include a statement such as, "Based on the data collected in your last session, we will not require any further testing. As indicated in the beginning, participation depends on a number of factors and not all participants qualify for the entire study."

Describe the procedures that you will use to recruit these participants. Be specific. How will potential subjects be identified? Who will ask for participation? If you intend to recruit using letters, posters, fliers, ads, website, email, PsyLink description, HIT, etc., copies must be included as attachments for stamped approval. Include scripts for intended telephone recruitment.

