### Surveys:

During the first visit, known as “Consent Visit 1”, participants will sign the consent form, complete the W-9 form and complete surveys. Participants will complete screening measures for anxiety, depression, and cognitive impairment. If they pass these screenings, they will be randomized into the intervention (self-affirmation + gain-framed messaging) or control group (loss-framed messaging only). In this visit and the next (Consent Visit 2) they will also complete neuropsychological and behavioral inventories. We expect testing to take about 3 hours total over the 2 sessions and will administer the assessments with breaks every ~40 minutes to reduce fatigue. They will complete behavioral inventories that capture individual differences in traits potentially predicting responsiveness to the intervention. These measures (listed in the attached spreadsheet) include validated questionnaires to assess factors like motivation for physical activity, self-efficacy for exercise, self-efficacy for walking, barriers to exercise, mood, conscientiousness and grit, growth mindset, loneliness, future time perspective, and purpose in life. Participants’ educational attainment and total personal income levels will also be collected to create a measure of socioeconomic status, as described by Hartanto et al. (2019). These questionnaires will be administered through REDCap, a “secure, HIPAA-compliant, web-based application... housed in a secure local data center, behind the Tufts Medical Center firewall, and all web-based information is encrypted” ([tuftsctsi.org/research-services/informatics/redcap-research-electronic-data-capture/](http://tuftsctsi.org/research-services/informatics/redcap-research-electronic-data-capture/)).

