158 such as Craigslist and Facebook. Potential participants are screened by phone. The Telephone
159 Interview of Cognitive Status (TICS) is used initially to screen cognitive function. Sitting Time
160 questionnaire [27] and International Physical Activity Questionnaire [28] are used for screening
161 physical activity engagement and sedentary behavior. Potential participants are asked a series of
162 questions relating to the inclusion/exclusion criteria and past medical history.
163

164 **Intervention**

165 ***Study timeline***

166 An illustration of the study timeline can be seen in Figure 1. Each participant undergoes a
167 baseline session (T1) one week before the beginning of the intervention. Informed consent is
168 obtained at baseline, during which participants specify whether they opt to participate in the MRI
169 scans or not. Randomization takes place after obtaining informed consent (T1) and participants
170 are assigned into either the intervention or control group. During the T1 visit, the participants
171 also undergo baseline testing including neuropsychological tests and neurobehavioral
172 inventories, which take about 3 hours in total. In order not to prime exercise for the baseline
173 physical activity level, inventories that are related to exercise and self-perception are not
174 administered during T1 visit. At baseline, participants wear an activPAL monitor on their thigh
175 to assess postural aspects of sedentary behavior including time spent sitting and lying and a
176 wrist-worn accelerometer on their non-dominant hand to assess physical activity (see physical
177 activity monitoring). Both monitors are worn for a week. One week later (T2), physical
178 assessments and the remaining neurobehavioral inventories related to exercise and self-
179 perception will be administrated, which takes about 1.5 hours. The intervention lasts 4 weeks,
180 during which participants receive daily intervention messages via email or smartphone.
181 Participants are fitted with the accelerometers again for a one-week mid-intervention period
182 (week 3). The post-intervention visit (T3) is scheduled at the beginning of the last intervention
183 week (week 4). After the last intervention week (T4), participants repeat the neurobehavioral
184 week (week 4). After the last intervention week (T4), participants repeat the neurobehavioral
185 week (week 4). After the last intervention week (T4), participants repeat the neurobehavioral

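### The Protocol credits a vital-signs check at screening that its criteria and described screening steps do not show, and it states no action on an abnormal pre-walk reading

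*Protocol*

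**What the plan says.** Protocol section K (Risks, Exercise) gives two linked reasons for regarding an adverse cardiovascular response as rare. The first is that "assessment of vital signs and history of heart disease are included in our screening procedures". The second is that "only those adults with satisfactory results as detailed in our eligibility criteria will be allowed to participate in experimental procedures for this study". The reader is therefore sent to the eligibility criteria to find the check.

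Those criteria are in section H, where the form's instruction is "Provide all inclusion and exclusion criteria". The heart-disease items there concern history and treatment, for example "Current treatment for congestive heart failure, angina, uncontrolled arrhythmia, DVT or other cardiovascular condition". The Screening Procedures describe a verbal telephone screen made up of demographic questions, "medical history questions in relation to inclusion and exclusion criteria" and self-reported activity. The SAP (Participants) likewise describes "questions relating to the inclusion/exclusion criteria and past medical history", together with the TICS and questionnaires on sitting time and physical activity. At Consent Visit 1 the Protocol (Surveys) adds a second stage: "Participants will complete screening measures for anxiety, depression, and cognitive impairment". Randomization follows for those who pass.

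Heart rate and blood pressure enter in section J. Under Accelerometry, participants report a resting heart rate for the fitness estimate. Under Physical Assessments, at Orange Visit 1 and Indigo Visit 3, they report supine heart rate after 10 minutes' rest, then do a warm-up and five tests. They report blood pressure and heart rate before and after the 6-minute walk.

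**The concern.** The risk section relies on a vital-signs assessment to argue that serious cardiac events will be rare, and the place it points to does not contain one. The three cardiovascular and clot exclusions depend on current treatment or a past event. Someone with an untreated or unrecognised problem can satisfy all three, and a vital-signs check is the kind of measure that might pick that person up.

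What is at stake is participant safety and the accuracy of what the IRB is told. The people concerned are sedentary and aged up to 95. They do a 6-minute walk, a chair stand and an 8-foot up-and-go in a trial whose activities are mostly completed at home. Staff who receive an abnormal reading just before the walk have no stated instruction to hold the test, repeat the reading or refer the participant.

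**Working it through.** There is no figure in the plan to reproduce. The check sets the risk statement beside the sections it depends on.

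1. **Eligibility criteria (Protocol H).** Legible inclusion criteria: 11. Legible exclusion criteria: 18. Total 11 + 18 = 29. Criteria naming heart rate, blood pressure or another vital sign: 0 of 29. Criteria covering cardiac events, clots or current cardiovascular treatment: 3 of 29, all among the exclusions. Each list also has one blank bullet in the text available.

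2. **Described screening elements.** Before consent: demographics, medical history, TICS, physical activity and sitting time, which is 5 (Protocol Recruitment Procedures and Screening Procedures; SAP Participants). At Consent Visit 1: anxiety, depression and cognitive impairment, which is 3 (Protocol Surveys). Total 5 + 3 = 8. Elements that include a vital sign: 0 of 8. The MRI metal-screening form is not counted.

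3. **Timing of the readings that do exist.** The Protocol randomizes after the Consent Visit 1 screens. The SAP (Study timeline) randomizes at T1 and puts the physical assessments at T2, one week later. The Protocol puts the first assessment at Orange Visit 1, after the baseline device week. The Accelerometry section names no visit for the resting heart rate, but it describes the same supine report that Physical Assessments places at Orange Visit 1. On the described order, the first readings come after randomization, so they cannot be the screening assessment the risk section refers to.

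4. **Actions attached to a reading.** Limits, holds, stops or referrals tied to heart rate or blood pressure in Physical Assessments or in the safeguards of section K: 0. The treatment of mood and cognition differs. The GDS, GAI and MoCA are scored immediately, screens in those domains must be passed before randomization, and clinically significant scores lead to referral.

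| Part of the risk statement | Counterpart in the text available |
|---|---|
| Heart-disease history at screening | Yes: medical-history questions and 3 exclusions |
| Vital signs at screening | None found (0 of 8 elements) |
| Satisfactory vital signs under the criteria | None found (0 of 29 criteria) |
| Action on pre-walk heart rate or blood pressure | None stated |

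**The case against.** The strongest objection is that absence is being argued from an incomplete file. The screening section summarises the call and defers to a telephone script; questionnaires and other forms are attachments; none was available. The blank bullet in the exclusion list falls directly after the cardiac-event item. This stands as a limit: the point is about what the text shows. It does not remove the mismatch, because the risk section cites the eligibility criteria and no legible criterion matches.

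Second, the plan has more protection than the bare counts suggest. Supine heart rate is already listed before the warm-up and all five tests. There is a general exclusion route: "If a participant requires exclusion due to information received during a visit, they will be contacted via telephone or email". Staff know an emergency protocol and meet to discuss safety concerns, exertion is rated around the walk, participants are not explicitly told to exercise, and fitness is estimated without an exercise test. All of this is accepted, and the heart-rate timing is used in the fix. None of it says what to do with an abnormal reading before the walk starts. The non-exercise fitness estimate does not cover the walk, chair stand and up-and-go, which are performed anyway.

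Third, numeric limits can reasonably sit in a visit manual. That is fair, and a citation would then be enough.

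Fourth, many of the 29 criteria (handedness, computer access, fluency) could never have carried a vital sign, so the denominator should not be read as a measure of severity. That also stands.

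**Conclusion.** The risk statement and the described design do not agree on vital signs. The size is 0 of 29 legible criteria and 0 of 8 described screening elements, with no stated action on the heart rate and blood pressure reported after randomization. This should be corrected because the plan relies on the safeguard when it calls the risk rare. As written, a participant with an abnormal reading could start the 6-minute walk.

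Three stronger readings are tempting and are not supported:

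- A reader might infer that no vital-signs rule exists anywhere, or that the IRB was misinformed. The attachments and blank bullets were not available, and the IRB may have seen more than the main text.
- A reader might infer that cardiac screening is absent. The history half of the statement is supported.
- A reader might infer a quantified excess risk or a threat to the trial's conclusions. The counts estimate no harm, nothing here touches sample size or error rates, and the walk test is not among the listed primary outcomes.

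The conclusion assumes that the legible lists are otherwise complete and that randomization precedes the physical assessment, as both documents describe.

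**What to change.** **Physical Assessments (Protocol J).** Take blood pressure together with the supine heart rate already reported, before the warm-up and first test. Use both as a go/no-go check, with limits set by the investigators and one repeat after rest. State how blood pressure is obtained at home. If a value stays outside the limits:

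- skip the 6-minute walk, chair stand and 8-foot up-and-go;
- refer the participant to their primary care physician, as section K already does for the GDS, GAI and MoCA;
- have the investigator decide whether the messages encouraging walking should continue;
- keep the participant's data in the primary analysis.

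The investigator's decision on the messages is needed because this check comes after randomization. Withholding only the tests would leave someone with persistently abnormal values still being encouraged to walk.

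**Exercise (Protocol K).** Replace the screening vital-signs clause with this check and keep the heart-disease-history clause. If an attachment already holds such a rule, cite it in both sections instead.

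**Cost.** Wording changes in two sections and a slightly earlier blood pressure reading. The Protocol does not say who supplies a monitor, so a home cuff and brief instruction may be needed. A few walk-test results will be missing, some because of false-alarm home readings.

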### Cognitive assessment and questionnaires

Some inconvenience and/or anxiety may occur due to time required to complete formal rating scales and questionnaires. The cognitive assessments impose some risk of emotional discomfort. Fatigue is associated with performing the cognitive tasks. The Geriatric Depression Scale, the Geriatric Anxiety Inventory, and the Montreal Cognitive Assessment may warrant a follow-up if the subject receives a clinically significant score on any of these items (e.g., >5 on the GDS). These items will be scored immediately after completion by the subject.

### ActiGraph physical activity monitor

Participants may experience red skin or discomfort from wearing the device around the wrist too tightly or for an extended period of time.

### ActivPAL physical activity monitor

Participants may experience skin irritation from the adhesive worn on the thigh. There is also a small risk of injury from shaving a portion of the right thigh at home in preparation for the study.

## MRI

It is possible that during the completion of the MRI scan, participants may become frustrated or fatigued. Some subjects experience discomfort associated with confinement and remaining stationary for a long period of time. Since the MRI is very noisy, there is minimal risk of hearing impairment. There is also the risk of injury related to metal attraction, since the MRI machine is a magnet. Some participants may become claustrophobic or anxious during a scan. Anxiety may continue even after the scan. Sometimes people feel lightheaded when they sit up after a scan. A clinically significant, unexpected disease or condition might be identified during the MRI scan. Additionally, there is a risk of unknown ferrous materials. The magnet of the MR system has a very strong magnetic field that is dangerous to a person entering the magnet room if they have certain metallic, electronic, magnetic, or mechanical implants, devices, or objects.

Describe in detail the safeguards that will be implemented to minimize risks. What follow-up procedures are in place if harm occurs? What special precautions will be instituted for vulnerable populations?

